10.4 Pregnancy Reporting

Female patients must be instructed to notify the Investigator immediately if they become pregnant or if they suspect to be pregnant during the trial. The Sponsor has a responsibility to monitor the outcome of all pregnancies reported during the clinical trial.

Male patients must be instructed to notify the Investigator immediately if their partner becomes pregnant or suspects to be pregnant. The Sponsor has a responsibility to monitor the outcome of all pregnancies reported during the clinical trial. During an information meeting at the trial site, the patient's partner will be fully informed by a physician of her participation in capturing the outcome data, and will be asked to provide her written consent.

The Investigator must report all information on pregnancies, including AEs in the patient/patient's partner, the fetus, and newborn infant/ toddler. The pregnancy report must be forwarded to the Sponsor preferably electronically as PDF or by fax.

The Investigator must follow the pregnancy until the pregnancy outcome and the newborn infant(s) until the age of 1 month. The Investigator must collect information on the pregnancy and pregnancy complications as well as the pregnancy outcome including the health of the newborn infant(s) on the pregnancy forms.

The following must be collected:

- Initial information of the pregnancy
- Information on the outcome of the pregnancy, including the health status of the newborn infant(s) at the age of 1 month
- All AEs in connection with the pregnancy and pregnancy outcome must be reported on the pregnancy forms. It must be clear in the description if the event occurs in the patient/patient's partner, the fetus, or the newborn infant.

Clinical Trial Protocol
ZP4207-16051

Version number: 3.0
Amendment 2.0
Date: 03 August 2016

- All SAEs in connection with the pregnancy and pregnancy outcome must be reported on the pregnancy forms following the same timelines as required for other SAEs. It must be clear in the description if the event occurs in the patient/patient's partner, the fetus, or the newborn infant.

The SAEs that must be reported include abnormal outcome – such as congenital anomalies, fetal death, and termination of pregnancy (spontaneous or elective abortion), including any anomalies of the fetus observed at gross examination or during autopsy – as well as other pregnancy complications (ectopic pregnancy) fulfilling the criteria of an SAE.

10.5 Hypoglycemia

Hypoglycemia will be regarded as an AE and will be recorded and documented on an AE Form. For the purposes of AE reporting, the following definitions of hypoglycemia will be used:

- Symptomatic hypoglycemia: an event during which typical symptoms of hypoglycemia are accompanied by a BG concentration ≤ 70 mg/dL
- Asymptomatic hypoglycemia: an event not accompanied by typical symptoms of hypoglycemia but with a BG concentration ≤ 50 mg/dL
- Severe hypoglycemia: an event requiring assistance of another person to actively administer carbohydrates, glucagon, or take other corrective actions

10.6 Safety Monitoring

10.6.1 Data and Safety Monitoring Board

An external DSMB will oversee the conduct of the trial, as set forth in the DSMB Charter. Additionally, the DSMB will be informed in the event of any serious and unexpected AEs. The DSMB will be informed if there are any changes to the trial protocol that could significantly impact the safety or scientific validity of the trial. A final DSMB meeting will convene after the completion of the trial.

The participation of individual patients will be discontinued if they experience:

- Seizure or unconsciousness associated with hypoglycemia and associated with participation in the trial
- Persistent nausea and vomiting thought to be related to glucagon dosing associated with participation in the trial
- Hospitalization associated with participation in the trial
- Pregnancy
- Diabetic ketoacidosis

If more than 1 patient must be withdrawn from the trial for these reasons, the trial will stop and a vote of the DSMB will be required to restart it. All AEs that are serious and unexpected but related will be reported to the DSMB within 5 working days.

Note that patients may discontinue participation at any time. Patients may be removed from the trial for other reasons, for instance, failure to comply with trial procedures or intercurrent illness that is unrelated to the BP but that precludes safe participation. Discontinuation of participation for these reasons will not contribute to a decision to discontinue the trial.

Clinical Trial Protocol
ZP4207-16051

Version number: 3.0
Amendment 2.0
Date: 03 August 2016

10.6.2 Zealand Pharma Safety Committee

The internal Zealand Pharma Safety Committee is constituted to perform ongoing safety surveillance of clinical trials within ZP4207, including this trial.

If safety signals are observed either based on reported SAEs, periodic review of laboratory parameters, planned review of all AEs reported between the safety committee meetings, or on notification of significant findings, the Safety Committee will take appropriate measures to safeguard the patients.

11 STATISTICS

11.1 Analysis Populations

The following analysis sets are defined in accordance with the ICH-E9 guidance:

The Full Analysis Set is based on the intention-to-treat principle and includes all randomized patients. In exceptional cases, patients from the Full Analysis Set may be excluded (will be decided in the database review [DBR] meeting). In such cases, the exclusion will be justified and documented. Patients will contribute to the evaluation "as randomized."

The Per-Protocol Set includes all patients of the Full Analysis Set who completed the trial without any major protocol violations. Patients in the Per-Protocol Set will contribute to the evaluation "as treated." This analysis will only be used if it is different than the Full Analysis Set.

The Safety Analysis Set includes all patients receiving at least 1 dose of the IMP. Patients in the Safety Analysis Set will contribute to the evaluation "as treated."

Analyses of efficacy endpoints will be based on the Full Analysis Set (and the Per-Protocol Set if necessary). This decision will be made in the DBR meeting. The analysis of the safety endpoints will be based on the Safety Analysis Set.

Before data are released for statistical analysis, a blinded review of all data will take place to identify protocol deviations that may potentially affect the results. At this time, it will be determined if patients and/or data should be excluded from the analysis. Furthermore, outliers will be identified by data review according to ICH-E9.

Obviously erroneous data points may be excluded from the analyses or re-analyzed (e.g., serum concentrations). The decision to re-analyze or exclude data points from the statistical analysis is the joint responsibility of the Sponsor, the Principal Investigator, and the Trial Statistician.

The patients or observations to be excluded and the reason for their exclusion will be documented and signed by those responsible prior to database release. The documentation will be stored together with the remaining trial documentation. The patients and observations excluded from analysis sets, and the reason for this, will be described in the clinical trial report.

Clinical Trial Protocol
ZP4207-16051

Version number: 3.0
Amendment 2.0
Date: 03 August 2016

11.2 Statistical Methods

Medpace will be responsible for the statistical analysis. The statistical planning and conduct of analyses of the data from this trial will follow the principles defined in relevant ICH guidelines and Medpace's biostatistical standard operating procedures (SOPs). A general description of the statistical methods to be used is given in this section, specific details will be provided in the Statistical Analysis Plan (SAP), which will be prepared before database lock. All statistical analyses will be performed using SAS® (SAS Institute Inc., Cary, North Carolina, USA), version 9.4 or later.

11.2.1 Analysis of Safety

The following variables will be evaluated according to treatment for safety purposes:

Adverse Events

All AEs will be coded using the latest version of Medical Dictionary for Regulatory Activities (MedDRA). Individual AEs will be presented in a listing including relationship to trial product/device, severity, and treatment period at onset. If more than 20 treatment-emergent AEs (AEs with onset after [first] dosing at Visit 3 until the Follow-up Visit 6) are registered, a summary table including number of AEs, number of patients with at least 1 AE, and percentage of exposed patients with at least 1 AE will be made by system organ class and treatment period at onset.

Local Tolerability

Local tolerability at the injection site will be summarized using descriptive statistics as appropriate.

Laboratory Safety Assessments

Laboratory assessments will be summarized. A listing of abnormal values will be provided.

Physical Examination

A frequency table will show the number and percentage of physical examination results.

Vital Signs

Vital signs will be summarized using descriptive statistics.

12-lead ECG

The Investigator's evaluations of 12-lead ECGs will be summarized and abnormal individual evaluations will be listed together with the Investigator's comments. Changes in 12-lead ECG between measurements will be recorded as AEs if the Investigator judges them to be clinically significant.

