- Patients will be asked to rate any nausea and/or infusion site pain on 10 cm visual analog scales (VAS) at the beginning of the visit once the infusion sites have been placed but no drug has yet been administered, then approximately at the top of every hour during the visit, and at the end of the visit. Trial staff will also evaluate their infusion sites to document any erythema or edema at the same times. If moderate or severe pain is reported or swelling or redness occurs at the infusion site, the infusion site will be replaced in a different location. If moderate or severe pain, swelling, or redness continues at the old site for more than 30 minutes after the infusion site is removed, or if moderate or severe pain, swelling, or redness occurs at the new site, all infusion sites will be removed and the patient will be discontinued from the study. Any such symptoms will be followed until resolution.
- From the start of closed loop control until approximately Hour 3, the patients will continue to fast.
- Between approximately Hour 3 and Hour 4, patients will be provided with a lunch meal of their choice in the Diabetes Research Center from a menu of choices from nearby restaurants. They will be asked to choose a meal that is a "typical meal" for them. The content of their meal will not be restricted in any way, with the exception that the

Clinical Trial Protocol
ZP4207-16051

Version number: 3.0
Amendment 2.0
Date: 03 August 2016

number of carbohydrates should be in the “typical” range for them at lunch, and that they must eat the same meal at the same time during both visits.

- At approximately 15 minutes before the meal, patients will administer a bolus for the meal with their own insulin pump based on the carbohydrate count for the meal.
- After lunch is completed, the patients will not be allowed any carbohydrate intake (non-caloric drinks will be permitted) until the trial is completed (except as necessary to treat hypoglycemia), to allow the BP to control the post-prandial BG without further interruption.
- Between approximately Hour 6 and Hour 7, the patients will start a period of structured exercise.
- At the start of the exercise period, patients will restore their normal basal insulin profile so that they will not have elevated insulin levels at the end of the study period when they are to transition back to their usual care.

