An AE is any untoward medical occurrence in a trial patient administered an IMP and which does not necessarily have a causal relationship with the treatment. An AE can therefore be any unfavorable and unintended sign (e.g., an abnormal laboratory finding), symptom, or disease temporally associated with the use of an IMP, whether or not considered related to the IMP. Patients should be instructed to report any AE they experience to the Investigator.

Clinical Trial Protocol
ZP4207-16051

Version number: 3.0
Amendment 2.0
Date: 03 August 2016

Note: This includes events from the first trial-related activity from Visit 3.

AEs for ZP4207 include:

- A clinically significant worsening of a concomitant illness
- A clinical laboratory abnormality which is clinically significant, i.e., any abnormality that suggests a disease and/or organ toxicity and is of a severity that requires active management. Active management includes active treatment or further investigations, for example, change of medicine dose or more frequent follow-up due to the abnormality.
- Hypoglycemic episodes
- Injection site reactions

The following should **not** be recorded as AEs, if recorded prior to randomization (on the Screening Form or the eCRF):

- Pre-planned procedure, unless the condition for which the procedure was planned has worsened from the first trial-related activity from Visit 3.
- Pre-existing conditions found as a result of screening procedures (pre-existing conditions should be reported as medical history or concomitant illness).

For known (listed) AEs for Glucagon and Humalog, please refer to SPC for [Glucagon](#) and [Humalog](#).

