10.1.2 Precautions

Normal precautions taken for a human trial will be taken during this trial. Qualified and well-trained physicians and medical staff will instruct the patients. During a patient's participation in the trial, the Investigator should ensure that adequate medical care is provided to the patient for any AEs, including clinically significant laboratory values related to the trial. The Investigator should inform the patient when medical care is needed for intercurrent illnesses of which the Investigator becomes aware.

For further information on safety precautions for ZP4207, Lilly glucagon, Lilly Humalog, and the iLet, please refer to the current version of the Investigator's Brochure (IB) for ZP4207

Clinical Trial Protocol
ZP4207-16051

Version number: 3.0
Amendment 2.0
Date: 03 August 2016

(Zealand Pharma A/S, 2015, or any updates hereof), and the SPC for Glucagon (Eli Lilly, 2012) and Humalog (Eli Lilly, 2015), respectively.

10.1.3 **Assessment of Adverse Events by the Investigator**

Intensity of an Adverse Event

The maximum intensity (severity) of all AEs must be assessed by the Investigator and documented. Severity should be graded when the AE outcome is known:

- **Mild:** A type of AE that is usually transient and may require only minimal treatment or therapeutic intervention. The event does not generally interfere with usual activities of daily living.
- **Moderate:** A type of AE that is usually alleviated with additional specific therapeutic intervention. The event interferes with usual activities of daily living, causing discomfort but poses no significant or permanent risk of harm to the patient.
- **Severe:** A type of AE that interrupts usual activities of daily living, or significantly affects clinical status, or may require intensive therapeutic intervention.

A “severe” reaction does not necessarily deem the AE as “serious,” and an SAE may not be “severe” in nature.

Causality Relationship to IMP

Insulin (insulin lispro, Lilly Humalog), glucagon (glucagon for injection, Eli Lilly), and ZP4207 are all regarded as IMP.

The causality of each AE should be assessed by the Investigator according to the following classification:

- **Related:** Good reason and sufficient documentation to assume a causal relationship.
- **Not related:** No relationship to trial product can be established.

Outcome of an Adverse Event

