10.3 Adverse Event Reporting – Procedures for Investigators

The Principal Investigator and co-investigators will review any AEs and report any SAEs to the Sponsor as soon as possible and within 24 hours of obtaining knowledge of the event. The Principal Investigator and co-investigators will promptly report AEs to the Partner’s Institutional Review Board (IRB) and to the BU IRB (unless oversight is ceded by the BU IRB to the Partners IRB), in accordance with local requirements.

[name] is the Sponsor of the Investigational Device Exception for the BP and Zealand Pharma A/S is the Sponsor of the IND for ZP4207.

Reports of AEs will be submitted to the FDA in compliance with the terms of the Code of Federal Regulations.

All events meeting the definition of an AE must be collected and reported from the first trial-related activity from Visit 3 until the end of the post-treatment follow-up period. At each contact with the site (visit or telephone, excluding safety visits, where the patient is not seeing the Investigator or staff [e.g., visits to the laboratory], the patient must be asked about AEs. All AEs, either observed by the Investigator or reported by the patient, must be recorded by the Investigator and evaluated.

The Investigator should record the diagnosis, if possible. If no diagnosis can be made, the Investigator should record each sign and symptom as individual AEs.

Clinical Trial Protocol
ZP4207-16051

Version number: 3.0
Amendment 2.0
Date: 03 August 2016

All AEs must be recorded by the Investigator. One single AE Form must be used per AE from start to resolution. For SAEs, the SAE Form must also be completed.

AE information should include the following:

- Patient identification number on all pages
- Date and time of treatment start
- Date and time of onset and date of outcome
- Date and time of Investigator's first information on the (S)AE
- Seriousness
- Severity
- Causal relationship with IMP ZP4207
- Causal relationship with IMP insulin
- Causal relationship with IMP glucagon
- Causal relationship with medical device
- Causal relationship with procedures
- Interruption or withdrawal of treatment with IMP or medical device and other measures taken
- Outcome

All AEs are coded; details are described in the trial specific Data Management Plan.

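### AEs are counted and allocated by onset only, so one that worsens on drug, or under the second product of the cross-over, is not counted where it worsened

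*Protocol*

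**What the plan says.** All of this is in the current text (version 3.0).

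- **Treatment-emergent.** Section 11.2.1 makes a summary table conditional: "If more than 20 treatment-emergent AEs (AEs with onset after [first] dosing at Visit 3 until the Follow-up Visit 6) are registered". The definition in the bracket rests on onset; it has no limb for worsening.
- **Allocation.** In that table, the "percentage of exposed patients with at least 1 AE will be made by system organ class and treatment period at onset". The listing follows the same rule: "Individual AEs will be presented in a listing including relationship to trial product/device, severity, and treatment period at onset".
- **Record unit.** Section 10.3: "One single AE Form must be used per AE from start to resolution". Under Section 10.1.1 an event that turns serious stays the same AE and gains an SAE Form.
- **Grade.** Section 10.1.3: "The maximum intensity (severity) of all AEs must be assessed by the Investigator and documented". Grading takes place once the outcome has been established.
- **Collection window.** Section 10.3 starts AE collection with the opening trial procedure at Visit 3, which precedes dosing. Section 7.4.1 has nausea and site pain rated "at the beginning of the visit once the infusion sites have been placed but no drug has yet been administered".
- **Gap between products.** Section 7.4 allows 24 hours to 3 weeks between the treatment visits.
- **Role of the data.** AE counts and types head the list of primary endpoint components in Section 8.1, and Section 11.2.1 says safety variables are evaluated by treatment.

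**The concern.** In a parallel-group trial an onset-only definition mostly loses pre-existing events that get worse. In a two-product cross-over it does something further: it decides which product an event belongs to. With one form, one maximum grade and one period at onset, an event that spans both visits has a single home, the first period, whatever happened later.

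The comparison at stake is ZP4207 against marketed glucagon on the first component of the primary endpoint, in a trial so small that one event is visible in the table. The peak severity of an event can also be filed under the product that did not produce it.

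**Working it through.** The protocol gives no AE figure to reproduce and no formal sample size calculation (Section 11.2.4), so the check consists of following two events through the rules and then doing the proportion arithmetic.

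**Event A: starts at Visit 3 before dosing, worsens on drug.**
1. It is collected, because collection has already begun (10.3).
2. Its onset is before first dosing, so it is not treatment-emergent (11.2.1), and the later worsening does not change that.
3. It appears in the listing with causality and its maximum grade, but not in the treatment-emergent table.

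This gap exists at Visit 3 only. Any onset at Visit 4 is already after first dosing.

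**Event B: starts mild under the first product, is still present at Visit 4, becomes severe under the second.**
1. One form covers it from start to end (10.3).
2. The form carries one grade, severe (10.1.3).
3. Listing and table use "severity, and treatment period at onset", so it is one severe AE of the first period and nothing in the second.

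**Do other rules catch the worsening?** Section 10.1 counts "A clinically significant worsening of a concomitant illness" as an AE, but Section 7.2.1 describes concomitant illness as illness present at screening, so an event that begins at Visit 3 or later is outside it. Section 10.1 also makes a laboratory abnormality needing active management an AE, and Section 11.2.1 does the same for clinically significant ECG changes between measurements. Neither reaches an ordinary symptom such as headache.

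**Arithmetic.** Section 11.2.4 expects 10 to 12 randomized patients. Assume all receive both products, one patient is affected, and that patient has no other AE on the product concerned. One patient is 1/10 = 10.0 points, or 1/12 = 8.3 points.

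| Event | Rule as written | Onset or worsening counted | Change in one product's incidence |
|---|---|---|---|
| A | 0/10 (0/12) on the Visit 3 product | 1/10 (1/12) | 10.0 (8.3) points |
| B, first product | 1/10 (1/12) | 1/10 (1/12) | 0 |
| B, second product | 0/10 (0/12) | 1/10 (1/12) | 10.0 (8.3) points |

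For event B the between-product difference is 10.0 (8.3) points as written and 0 when worsening is counted. The severe grade moves from the first product to the second.

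**The case against.** The case against has real weight.

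- **Nothing is hidden from the listing.** Section 11.2.1 lists individual AEs without restricting them to treatment-emergent ones, and Section 10.3 asks for causality separately for ZP4207, insulin, glucagon, device and procedures. A reader might infer that a drug effect can vanish altogether; it cannot. This stands. It does not change the counts or the period allocation, which make no use of causality.
- **The likeliest symptoms are scored independently.** Nausea and pain VAS and Draize scores are taken before drug, hourly and at visit end, at both visits (7.4.1, 7.4.2), and are primary endpoint components themselves. Section 7.4.1 also has a red or swollen site moved, and discontinues the patient if certain reactions persist or recur, which largely rules out carry-over of site reactions to Visit 4. This stands, and confines the gap mainly to other AEs.
- **The table may never be made.** It needs more than 20 treatment-emergent AEs. True, but the listing, which is always made, uses the same period at onset.
- **Detail belongs in the SAP, and forms can be updated.** Section 11.2 leaves specifics to the SAP, and Section 10.1.1 allows follow-up information on the AE form. A reader might infer that the SAP could repair nothing. That goes too far: it could reword the definition, and the VAS and Draize scores would be available to it. For other AEs, however, the protocol does not require the time of worsening or an earlier grade, so the SAP could not count on having them.
- **The size is easily overstated.** A reader might infer a 20-point swing for event B, as if 1/10 versus 0/10 should become 0/10 versus 1/10. The event did begin under the first product and stays counted there, so the correction is 10 points.

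**Conclusion.** The point holds within limits. The protocol itself fixes an onset-only rule that misplaces worsening in a two-product cross-over: event A is left out of the treatment-emergent table, and event B is counted in the first period only, at a severity reached in the second. Each such event changes one product's any-AE incidence by 10 points (8.3 with 12 patients).

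This assumes that the treatment period identifies the product given in it, that every patient receives both products, and that the affected patient has no other AE on the product concerned. How often such events occur cannot be derived from the document; it is probably low, since treatment visits last about 8 hours and the symptoms most expected are scored separately. The case for acting rests on the event belonging to the first primary endpoint component and on the small cost, not on a large expected bias.

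**What to change.** - **Section 11.2.1:** define treatment-emergent for each treatment period as an AE that starts, or increases in intensity, after dosing starts in that period. Allocate it to the product in use at that time, in both the table and the listing.
- **Section 10.3:** when an AE present before dosing at Visit 3, or ongoing at Visit 4, worsens after dosing starts, require either a new AE record linked to the first (own start time, intensity and causality) or a dated intensity change on the existing form.
- **eCRF completion guide:** one line to match.

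The cost is two sentences, the guide line and a few more AE records. Linked records must be recognizable as such, so that total event counts can be read with and without them. The change should precede data collection, because a worsening that was not graded and dated when it happened cannot be reliably reconstructed. No dosing or clinical management rule is affected.
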